15.3 ST. GEORGE'S RESPIRATORY QUESTIONNAIRE

ST. GEORGE'S RESPIRATORY QUESTIONNAIRE ENGLISH FOR THE UNITED STATES

ST. GEORGE'S RESPIRATORY QUESTIONNAIRE (SGRQ)

This questionnaire is designed to help us learn much more about how your breathing is troubling you and how it affects your life. We are using it to find out which aspects of your illness cause you the most problems, rather than what the doctors and nurses think your problems are.

Please read the instructions carefully and ask if you do not understand anything.

Do not spend too long deciding about your answers.

Before completing the rest of the questionnaire:					
Please check one box to show how you describe your current health:	Very good	Good	Fair	Poor	Very poor

Copyright reserved

[name], PhD FRCP Professor of Respiratory Medicine, St. George's University of London, [name].

[contact] [contact]

Please	e describe how often your respiratory problen	ns have a	ffected yo	u over the	e past 4 wee	ks.
		Please check (✓) one box for each question				uestion:
		almost every day	several days a week	a few days a month	only with respiratory infections	not at all
1.	Over the past 4 weeks, I have coughed:					
2.	Over the past 4 weeks, I have brought up phlegm (sputum):					
3.	Over the past 4 weeks, I have had shortness of breath:					
4.	Over the past 4 weeks, I have had wheezing attacks:					
5.	How many times during the past 4 weeks have severe or very unpleasant respiratory attacks?	you suffer	ed from			
	severe or very unpreasant respiratory attacks:			Pleas	se ch ec k (✓)	one:
			more t	than 3 time	es 📙	
				3 time		
				2 time		
				1 tim		
			none	e of the tim	ie 🗀	
6.	How long did the worst respiratory attack last? (Go to Question 7 if you did not have a severe	attack)				
		,			se check (✓)	one:
				eek or mo		
			30	r more day 1 or 2 day		
			less	s than a da		
7.	Over the past 4 weeks, in a typical week, how n	nany good	d days			
	(with few respiratory problems) have you had?			Pleas	se check (✓)	one:
			No	good day		
			1 or 2	2 good day	/s 🗌	
			3 or 4	4 good day	/s	
		near	ly every da	ay was goo	od 🗌	
			every da	y was goo	od \square	
8.	If you wheeze, is it worse when you get up in the	e morning]?			
				Pleas	se check (✓)	one:
					lo 📙	
1				Yε	es 🗀	

Section 1	
	on? Please check (✓) one: ost important problem I have es me quite a lot of problems Causes me a few problems Causes no problems
Section 2 These are questions about what activities usually management	o or made me change my job oroblems do not affect my job oroblems
	ach statement please check ✓) the box that applies to you these days: True False □

Section 3				
These are more questions about your cough and shortness of breath these days.				
For each statement please check (✓) the box that applies to you these days :				
True False				
Coughing hurts				
Coughing makes me tired				
I am short of breath when I talk				
I am short of breath when I bend over				
My coughing or breathing disturbs my sleep \qed				
I get exhausted easily				
Section 4				
These are questions about other effects that your respiratory problems may have on you these days.				
For each statement, please				
check (✓) the box that				
applies to you these days : True False				
True False My cough or breathing is embarrassing in public				
My respiratory problems are a nuisance to my family, friends or neighbors				
I get afraid or panic when I cannot catch my breath				
I feel that I am not in control of my respiratory problems				
I do not expect my respiratory problems to get any better				
I have become frail or an invalid because of my respiratory problems				
Exercise is not safe for me				
Everything seems too much of an effort				
Section 5				
These are questions about your respiratory treatment. If you are not receiving treatment go to section 6.				
For each statement, please check (✓) the box that applies to you these days:				
True False				
My treatment does not help me very much \Box				
I get embarrassed using my medication in public				
I have unpleasant side effects from my medication \Box				
My treatment interferes with my life a lot				

Section 6				
These are questions about how your activities migh	t be affecte	ed by your r	espirator	y problems
		ach stateme the box tha se of your i	t applies t	
			True	False
I take a long time to ge				
I cannot take a bath or shower, or I tal				
I walk slower than other people my	age, or I st	top to rest		
Jobs such as household chores take a long time, or	I have to st	op to rest		
If I walk up one flight of stairs, I have	e to go slow	ly or stop		
If I hurry or walk fast, I have	to stop or s	low down		
My breathing makes it difficult to do things such as walk up stairs, light gardening such	h as weedir			
My breathing makes it difficult to do things such a dig in the garden or shovel snow, jog or walk brisk		per hour),		
My breathing makes it difficult to do thing manual work, ride a or pl		swim fast,		
Section 7 We would like to know how your respiratory problen	ns usually	affect your	daily life.	
the box th	at applies t	olease checl o you becau / problems :	ise of	
	True	False		
I cannot play sports or do other physical activities				
Learnet as out for entertainment or regrestion				
I cannot go out for entertainment or recreation				
I cannot go out of the house to do the shopping				
9				

Here is a list of other activities that your respiratory problems may prevent you from do not have to check these, they are just to remind you of ways your shortness of baffect you):	
Going for walks or walking the dog	
Doing activities or chores at home or in the garden	
Sexual intercourse	
Going to a place of worship, or a place of entertainment	
Going out in bad weather or into smoky rooms	
Visiting family or friends or playing with children	
Please write in any other important activities that your respiratory problems may stop doing:	
Now please check the box (one only) that you think best describes how your respirat affect you:	ory problems
It does not stop me from doing anything I would like to do	
It stops me from doing one or two things I would like to do	
It stops me from doing most of the things I would like to do	
It stops me from doing everything I would like to do	
Thank you for completing this questionnaire. Before you finish would you please make sur answered all the questions.	re that you have

# **ABBREVIATIONS AND DEFINITIONS**

6MWD	6-Minute Walk Distance
6MWT	6-Minute Walk Test
AE	Adverse event
ANCOVA	Analysis of covariance
BMI	Body mass index
BOCF	Baseline Observation Carried Forward
СНР	Chronic Hypersensitivity Pneumonitis
CPFE	Combined Pulmonary Fibrosis and Emphysema
CSR	Clinical study report
СТ	Computed Tomography
CTD	Connective tissue disease
DLCO	Lung diffusion capacity
DMC	Data Monitoring Committee
DSP	Distance saturation product
ECG	Electrocardiogram
eCRF	Electronic Case Report Form
ET	Early termination
FEV 1	Forced expiratory volume in 1 second
FVC	Forced vital capacity
HR	Heart rate
ICF	Informed consent form
IIP	Idiopathic interstitial pneumonia
ILD	Interstitial lung disease
ITT	Intent-to-treat
LOCF	Last observation carried forward
LRCF	Last rank carried forward
MedDRA	Medical Dictionary for Regulatory Activities
MMRM	Mixed model repeated measurement
NT-proBNP	N-Terminal pro-brain natriuretic peptide
PAPm	Pulmonary artery pressure mean
PCWP	Pulmonary capillary wedge pressure
PFT	Pulmonary function test
PH	Pulmonary hypertension
PH-ILD	Pulmonary hypertension associated with interstitial lung disease

P-R	Time between P wave and beginning of QRS complex in electrocardiography
PT	Preferred Term
PVR	Pulmonary vascular resistance
Q-T	Electrocardiographic interval from beginning of QRS complex to end of the T wave
QTc	QT interval corrected for heart rate
QRS	Electrocardiographic wave interval
RHC	Right heart catheterization
RMST	Restricted mean survival time
SAE	Serious adverse event
SAP	Statistical analysis plan
SGRQ	St. George's Respiratory Questionnaire
SOC	System Organ Class
$SpO_2$	Saturation of Peripheral Capillary Oxygenation
TLC	Total lung capacity
WHO-DD	World Health Organization Drug Dictionary
WU	Wood Units

### 1 **PREFACE**

This plan provides further details of the planned analyses for the RIN-PH-201 study as presented in the study protocol. This plan, based on the original RIN-PH-201 study protocol dated 21 Oct 2015 and the subsequent study protocol amendments (latest version study protocol amendment 3 dated 15 February 2017), provides further details of the planned analyses stated in the study protocol as well as any additional planned analyses. Additional post hoc or unplanned analyses that are not defined in this statistical analysis plan (SAP) may be performed. Such analyses will be documented in the clinical study report (CSR).

### 2 STUDY OBJECTIVES AND ENDPOINTS

The primary objective of this study is to evaluate the safety and efficacy of inhaled treprostinil in subjects with Pulmonary Hypertension (PH) associated with Interstitial Lung Disease (ILD), including Combined Pulmonary Fibrosis and Emphysema (CPFE).

# 2.1 PRIMARY ENDPOINT

The primary endpoint is the change in 6-Minute Walk Distance (6MWD) measured at peak exposure from Baseline to Week 16.

### 2.2 SECONDARY ENDPOINTS

The secondary endpoints are:

- 1. Change in peak 6MWD from Baseline to Week 12
- 2. Change in plasma concentration of N-terminal pro-brain natriuretic peptide (NT-proBNP) from Baseline to Week 16
- 3. Change in trough 6MWD from Baseline to Week 15

# 2.3 EXPLORATORY ENDPOINTS

Exploratory endpoints are:

- 1. Change in peak 6MWD from Baseline to Week 4
- 2. Change in peak 6MWD from Baseline to Week 8
- 3. Change in quality of life as measured by the St. George's Respiratory Questionnaire (SGRQ) from Baseline to Week 16
- 4. Time to clinical worsening will be evaluated as an exploratory endpoint from the time to randomization until 1 of the following criteria are met:

#### Confidential

- a. Hospitalization due to a cardiopulmonary indication
- b. Decrease in 6MWD >15% from Baseline directly related to disease under study, at 2 consecutive visits, and at least 24 hours apart
- c. Death (all causes)
- d. Lung transplantation
- 5. Change in distance saturation product (DSP) from Baseline to Week 16

Exploratory endpoints of optional evaluation are change in biomarkers from Baseline to Week 16, and optional evaluation of whole genome sequence. They will be specified in separate documents and not covered in this statistical analysis plan.

# 2.4 SAFETY ENDPOINTS

Safety endpoints will be used to evaluate safety based on the following assessments:

- 1. Adverse events (AEs)
- 2. Oxygenation:
  - a. Pulse oximetry (saturation of peripheral capillary oxygenation [SpO2])
  - b. Supplemental oxygen requirement (L/min)
- 3. Pulmonary function:
  - a. Forced expiratory volume in 1 second (FEV1)
  - b. Forced vital capacity (FVC)
  - c. Total lung capacity (TLC)
  - d. Lung diffusion capacity (DLCO)
- 4. Clinical laboratory parameters
- 5. Vital signs
- 6. Electrocardiograms (ECG)
- 7. Hospitalization due to a cardiopulmonary indication.
- 8. Exacerbations of underlying lung disease; defined as an acute, clinically significant, respiratory deterioration characterized by evidence of new widespread alveolar abnormality.

### **3** STUDY DESIGN

This is a multicenter, randomized, double-blinded, placebo-controlled, 16-week, parallel group study. Subject eligibility will be based on the inclusion and exclusion criteria described in Section 4 of the protocol. Approximately 314 eligible subjects will be randomized to study

treatments (inhaled treprostinil or placebo) in a 1:1 ratio. Subjects will be stratified based on Baseline 6MWD ( $\leq$ 350 meters versus >350 meters).

Subjects will be treated with either inhaled treprostinil (6 mcg/breath) or placebo.

The study will consist of the following phases:

- Screening Phase: Prospective subjects will undergo a screening evaluation within 30 days prior to the Baseline Visit (randomization and first dose of study drug). During this phase, eligible subjects will sign the informed consent form (ICF) and undergo Screening assessments. The Screening and Baseline assessments may be combined if all entry criteria are satisfied within 48 hours prior to the first dose of study drug. Baseline pulmonary function tests (PFTs) and 6-Minute Walk Test (6MWT) used to confirm eligibility criteria may be performed on the same day but prior to the first dose of study drug.
- **Baseline Visit:** The Baseline assessments may be conducted over a 48-hour period prior to the first dose of study drug to allow for scheduling of all activities. Eligible subjects will undergo Baseline assessments, be assigned to a treatment group based on the randomization schedule, and receive the first dose of study drug (Day 1 is defined as the day the first dose of study drug is given). The Screening and Baseline assessments may be combined if all entry criteria are satisfied within 48 hours prior to the first dose of study drug. Baseline PFTs and 6MWT used to confirm eligibility criteria may be performed on the same day but prior to the first dose of study drug.
- **Treatment Phase:** The Treatment phase consists of 5 study visits to the clinic at Week 4, Week 8, Week 12, Week 15, and Week 16 (final study visit; at least 24 hours after the Week 15 Visit [final study visit/early termination {ET}]). Subjects will also be contacted at least weekly by telephone or email to assess subject tolerance to study drug, AEs, and changes to concomitant medications.

# 4 SEQUENCE OF PLANNED ANALYSES

#### Interim Safety Analyses

Interim safety analyses are intended to be performed according to the Data Monitoring Committee (DMC) Charter. In particular, interim safety analyses are planned following the enrollment of approximately 25%, 50%, and 75% of subjects in the study, or at least annually (whichever is sooner). All analyses will be prepared by an independent external consultant and reviewed only by the independent DMC as defined in the DMC Charter. The Sponsor will only have access to the blinded study data during this process. Interim efficacy analyses are not planned in this study.

# Dry-run Analysis Prior to Database Lock (Soft Lock)

At the completion of the study enrollment and prior to the database lock, a dry-run analysis is planned. This dry-run analysis utilizes a dummy randomization schedule in a blinded fashion. The purpose of the dry-run analysis is to verify programming of the analysis data sets and the planned tables, listings, and figures, and to identify any data issues. Programming and data issues identified through the dry-run process will be resolved prior to the database lock and study unblinding.

### Final Analysis after Database Lock and Study Unblinding

After the database has been quality assured and locked, the treatment assignments will be provided to the sponsor's project statistician by the central randomization service and all planned analyses described in this document will be performed. By intent, no changes will be made to the clinical database after unblinding. However, any changes that are deemed necessary, after unblinding, will be clearly documented in the CSR.

# 5 SAMPLE SIZE CONSIDERATIONS

Using an allocation ratio of 1:1 between inhaled treprostinil and placebo, a sample size of approximately 266 subjects (133 per treatment) would provide at least 90% power at a significance level of 0.05 (2-sided hypothesis) to detect a 30 meter between-treatment difference in the change from Baseline to Week 16 in 6MWD, assuming a standard deviation of 75 meters.

The total sample size will be approximately 314 subjects to account for a discontinuation rate of approximately 15%.

# 6 ANALYSIS POPULATIONS

The Intent-to-Treat (ITT) population is defined as all subjects randomized into the study who received at least 1 dose of study drug. All ITT subjects will be counted in the group to which they were randomized, regardless of the study drug they were given. All efficacy analyses will be performed on this ITT population, unless otherwise specified.

The Safety population is defined as all subjects enrolled into the study who received at least 1 dose of study drug. All Safety population subjects will be counted in the group corresponding to the study drug received, regardless of randomized assignment. All safety analyses will be performed on this Safety population, unless otherwise specified.

The Per-protocol population will include all subjects in ITT population, excluding subjects with major protocol deviations that may have an impact on the primary efficacy analyses. The major protocol deviations and the subject's exclusion from the Per-protocol population will be reviewed at a blinded data review meeting and documented prior to the database lock and the study unblinding.

### 7 INTERIM ANALYSES

There is no interim efficacy analysis for this study.

A DMC will be established for the study including physicians knowledgeable in the treatment of PH and a statistician. Throughout the course of the study the DMC will meet on a regular basis to monitor the safety of the study. Meetings will occur as outlined in the DMC Charter. All analyses will be prepared by an independent external consultant and reviewed only by the DMC as defined in the DMC Charter. The Sponsor will only have access to blinded study data during this process. The details regarding the interim safety analysis will be included in a separate statistical analysis plan.

### 8 GENERAL CONSIDERATIONS FOR DATA ANALYSES

All the data collected in the electronic Case Report Form (eCRF) will be listed. In general, listings will be sorted by treatment group, subject number, and scheduled assessment (if applicable). Listings will include assessment date, assessment time (if available), study day, and all relevant data collected in the eCRFs. For data collected on a fixed schedule, the assessment identifier or the nominal time point will also be included on the listing. Repeat or redundant observations within an assessment window and observations that do not fall within any predefined assessment window (and will, therefore, be excluded from summaries) will be flagged in these listings. Subjects who are not to be included in the analysis population (eg, Safety population, Per-protocol population) will be flagged.

In general, the data will be summarized by scheduled assessment (if applicable) within each treatment group. For continuous variables, summary statistics will include the mean, standard deviation, median, minimum, and maximum. For summaries of non-normal data such as 6MWD, interquartile range (lower quartile, upper quartile) may also be included. Minimums and maximums will be expressed using the level of precision in which the variable was collected. All other statistics will be rounded, using an additional decimal place than was collected. For discrete variables, summaries will include the frequency and percentage in each category. Percentages will be rounded to 1 decimal place. For all inferential analyses and descriptive comparisons, p-values will be rounded to 4 decimal places. Values less than 0.0001 will be denoted as <0.0001, and values greater than 0.9999 will be denoted as >0.9999 whenever practical, categories of discrete variables will be ordered and labelled as they appear in the eCRF, and all categories represented on the case report form will be included in summaries, even when they do not apply to any subjects in the study.

Unless otherwise specified, all statistical tests will be 2-sided at alpha level 0.05. All statistical calculations will be completed using SAS® Version 9.4 or above.

# 8.1 COVARIATES

The primary efficacy analyses of change in 6MWD at Week 16 will be adjusted for Baseline 6MWD (as a continuous variable). For sensitivity analyses of the primary efficacy endpoints and the secondary/exploratory endpoints with continuous variables, the baseline measure will always be the covariate.

### 8.2 EXAMINATION OF SUBGROUPS

For primary efficacy endpoints of change in 6MWD at Week 16, subgroup analyses will be performed. These subgroups will include:

- Etiology of ILD (Idiopathic Interstitial Pneumonia [IIP], Chronic Hypersensitivity Pneumonitis [CHP], Occupational, CPFE, Connective Tissue Disease [CTD], and Other)
- Baseline walk categories (≤350 meters versus >350 meters, ≤ median baseline 6MWD versus > median baseline 6MWD)
- ILD disease severity as measured by Baseline DLCO (<40% predicted versus ≥40% predicted)

- Sex (male versus female)
- Pulmonary Vascular Resistance (PVR) (<4 versus ≥4 Wood Units [WU])
- Age group (<65 years of age, 65 to <80 years of age, and  $\geq$ 80 years of age)
- Study drug dose at Week 16 (0 to 3 breaths, 4 to 6 breaths, 7 to 9 breaths, and 10 to 12 breaths)

No Type 1 error adjustments will be performed for these subgroup analyses.

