# 10.1.1.2 Primary Efficacy Analysis

All 6MWT data will be listed for all subjects. For each scheduled assessment, this listing will include the date test was performed (or date test was intended to be performed if subject is unable to attempt the test), start time of the test, nominal time point, last treatment dose, hours from last treatment dose to 6MWT start, if walk was attempted, total distance walked (in meters), whether subject received oxygen during the test, amount of supplemental oxygen, and any circumstances that adversely affected the walk (if any) including reason for not

attempting test (if any). The trough 6MWT measure will also be indicated. In addition, a listing of 6MWD with imputed values will be included for both peak and trough 6MWD data.

For the primary efficacy analysis, the effect of inhaled treprostinil versus placebo on change in peak 6MWD at Week 16 will be evaluated via analysis of covariance (ANCOVA). Change from Baseline in peak 6MWD is the dependent variable, and treatment and Baseline 6MWD are covariates in this ANCOVA model. Least squares means and standard errors for each treatment group, the least squares mean difference and its standard error, as well as a 95% confidence interval for the treatment group difference and p-value for treatment group comparison will be calculated from the ANCOVA model. This methodology will be carried out as follows:

- 1. Walk distances obtained after study drug termination or unblinding will be excluded (as described in Section 8).
- 2. Imputation rules in Table 8-1 will be applied.
- 3. The LOCF algorithm will be applied.
- ANCOVA will be conducted based on the pseudo SAS code: proc glm; class Treatment; model DistC = Treatment Dist0; run;

where DistC is the change from Baseline in peak 6MWD at Week 16 and Dist0 is the baseline measure of the 6MWD.

If the ANCOVA assumptions are violated, the primary efficacy analysis will be based on non-parametric analysis of covariance within the framework of the extended Cochran-Mantel-Haenszel test (Koch 1990, Koch 1998, Stokes 2000). Specifically, a Cochran-Mantel-Haenszel mean score test will be used on the standardized mid-ranks (ie, overall rank divided by the number of ranks +1, or "modified ridit" scores) of the residuals from an ordinary least squares regression with change from Baseline in peak 6MWD at Week 16 as a linear function of distance walked at Baseline (as a continuous variable). This methodology will be carried out as follows:

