# 10.1.1.3 Sensitivity and Subgroup Analyses

In order to analyze walk distances at each scheduled assessment, values for missing or excluded assessments up to and including Week 16 will be imputed according to rules described in Section 8.3.1.

To further support the robustness and assess the sensitivity of the primary efficacy analysis of change in peak 6MWD at Week 16 (provided that the primary analysis yields significant results), the above non-parametric and parametric analyses and summaries will be repeated using each of the following modifications (as data permit):

- The Per-protocol population will be used instead of the ITT population
- Missing data imputation using the LOCF method (based on peak values)
- Missing data imputation using the last rank carried forward (LRCF) method (based on peak values) (O'Brien 2005)
- Using only the observed values without imputation
- Including data collected after termination of the study drug
- ITT population excluding subjects with a reported exacerbation within 3 days of the Week 16 peak 6MWT measure
- Stratified by ILD etiology categories (IIP, CHP, Occupational, CPFE, and Other)
- Stratified by Baseline 6MWD categories (≤350 meters versus >350 meters, ≤median baseline 6MWD versus > median baseline 6MWD)
- Stratified by Baseline DLCO percent predicted (<40% versus  $\geq 40\%$ )
- Stratified by Baseline pulmonary vascular resistance (PVR) (<4 versus  $\geq 4$  WU)
- Stratified by sex (male versus female)
- Stratified by age group (<65 years of age, 65 to <80 years of age, and ≥80 years of age)
- Stratified by study drug dose at Week 16 (0 to 3 breaths, 4 to 6 breaths, 7 to 9 breaths, and 10 to 12 breaths).

A longitudinal data analysis using mixed model repeated measurement (MMRM) will also be performed to estimate the treatment difference in change in peak 6MWD at Week 16. The MMRM will include the change from Baseline in peak 6MWD as the dependent variable, treatment, week, and treatment by week interaction as fixed effects, and Baseline 6MWD as a covariate. An unstructured variance/covariance structure shared across treatment groups will be used to model the within-subject errors. An additional sensitivity analysis will be performed for percent change from Baseline to Week 16 in peak 6MWD using the same approach as the primary analysis method where the percent change from Baseline is calculated as

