# 15 LIST OF TABLES, LISTINGS AND FIGURES

# **15.1 LIST OF TABLES**

Table Number	Table Title
14.1.1	Summary of Subject Accountability
14.1.2	Summary of Analysis Population Information
14.1.3	Summary of Demographic Data
14.1.4	Summary of Baseline Characteristics
14.1.5	Summary of PH-ILD History
14.1.6.1	Summary of Entry Criteria Violations
14.1.6.2	Summary of Protocol Deviations
14.1.7	Summary of Randomization Information
14.1.8	Summary of Medical History
14.1.9	Summary of Concomitant Medications Ongoing at Baseline
14.1.10	Summary of Concomitant Medications Added During the Study
14.1.11	Summary of Study Drug Dosing and Exposure
14.1.12	Summary of Study Drug Treatment Compliance
14.2.1.1	Summary and Analysis of Peak 6MWD (meter) at Week 16 – Primary Efficacy Endpoint
14.2.1.2	Summary and Analysis of Peak 6MWD (meter) at Week 16 – Per Protocol Population
14.2.1.3	Summary and Analysis of Peak 6MWD (meter) at Week 16 with LOCF Imputation for Missing Data
14.2.1.4	Summary and Analysis of Peak 6MWD (meter) at Week 16 with LRCF Imputation for Missing Data
14.2.1.5	Summary and Analysis of Peak 6MWD (meter) at Week 16 with No Imputation for Missing Data
14.2.1.6	Summary and Analysis of Peak 6MWD (meter) at Week 16 Including Data Collected after Termination of Study Drug
14.2.1.7	Summary and Analysis of Peak 6MWD (meter) at Week 16 Excluding Subjects with a Reported Exacerbation within 3 Days of the Week 16 6MWD Measure
14.2.1.8	Analysis of Peak 6MWD (meter) at Week 16 Using Mixed Model Repeated Measurement (MMRM)
14.2.1.9	Summary and Analysis of Percent Change from Baseline to Week 16 in Peak 6MWD
14.2.1.10	Summary and Analysis of Peak 6-Minute Walk Distance (meter) at Week 16 by ILD Etiology Category
14.2.1.11.1	Summary and Analysis of Peak 6MWD (meter) at Week 16 by Baseline 6MWD Category (≤350 meters versus >350 meters)
14.2.1.11.2	Summary and Analysis of Peak 6MWD (meter) at Week 16 by Baseline 6MWD Category (≤baseline median meters versus>baseline median meters)

Table Number	Table Title
14.2.1.12	Summary and Analysis of Peak 6MWD (meter) at Week 16 by Baseline DLCO Percent Predicted
14.2.1.13	Summary and Analysis of Peak 6MWD (meter) at Week 16 by Baseline PVR
14.2.1.14	Summary and Analysis of Peak 6MWD (meter) at Week 16 by Sex
14.2.1.15	Summary and Analysis of Peak 6MWD (meter) at Week 16 by Age Group
14.2.1.16	Summary and Analysis of Peak 6MWD (meter) at Week 16 by Study Drug Dose at Week 16

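### Comparing arms within bands of Week 16 dose, which is set after randomisation, cannot support the robustness of the primary result

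*SAP*

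**What the plan says.** SAP 8.2 names the subgroups for change in peak 6MWD at Week 16. Most are baseline characteristics: ILD aetiology, baseline walk, DLCO, sex, PVR and age. The last is "Study drug dose at Week 16 (0 to 3 breaths, 4 to 6 breaths, 7 to 9 breaths, and 10 to 12 breaths"). The section adds "No Type 1 error adjustments will be performed for these subgroup analyses".

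SAP 10.1.1.3 gives the purpose. "To further support the robustness and assess the sensitivity of the primary efficacy analysis", and provided that analysis is significant, "the above non-parametric and parametric analyses and summaries will be repeated" under 13 modifications. One of them is "Stratified by study drug dose at Week 16". The analyses being repeated are treatment-versus-placebo comparisons; the lead model in SAP 10.1.1.2 is "class Treatment; model DistC = Treatment Dist0; run". For the covariate, SAP 8.1 says that "the baseline measure will always be the covariate". The planned output, Table 14.2.1.16, is a "Summary and Analysis of Peak 6MWD (meter) at Week 16 by Study Drug Dose at Week 16".

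The protocol (Synopsis and 6.1) starts every subject in both arms at 3 breaths four times daily. Doses then rise as tolerated towards a common target and maximum. Section 6.1 lets the investigator set the schedule for each subject in the light of tolerability and functional improvement. The SAP attaches no caveat to the dose bands.

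**The concern.** Randomisation makes the arms comparable as a whole and within strata fixed at baseline. It does not make them comparable within strata formed afterwards. A band of Week 16 dose selects subjects on something that treatment may have changed, through tolerability, and that may share causes with the outcome or respond to it, through frailty or functional improvement. Subjects on active drug who reach 10 to 12 breaths may then be a different kind of patient from placebo subjects who do so.

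What is at stake is interpretation. Consistent effects across dose bands would be read as confirming the primary result, and inconsistent effects as a dose response or a weakness. Either pattern could come from selection alone.

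**Working it through.** **The plan's own figure.** For a 30 m difference, SD 75 m, two-sided alpha 0.05 and 90% power, n per arm = 2 × (1.96 + 1.282)² × 75² / 30² = 131.4, rounded up to 132 (264 in total, against 266 stated). Power at 133 per arm is 90.4%. With 15% discontinuation, 133 / 0.85 = 156.5, so 157 per arm and 314 in total, as stated. Nothing here depends on dose.

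**Inputs for the illustration.** From the documents: SD 75 m, 157 per arm, the four bands and the 12-breath maximum. Everything else is assumed, because the documents give no dose distribution by arm. F is unmeasured frailty; F, e1, e2 and e3 are independent standard normal.

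- Change = 75 × (-0.4 F + √0.84 e1), with a true treatment effect of 0 m.
- Dose = 11 - L·F - shift (active arm only) + √(8 - L²) e2, rounded and limited to 0 to 12. A positive shift means lower doses on active drug.
- Baseline 6MWD (standardised) = -0.5 F + √0.75 e3.

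With L = 2, the placebo shares of the bands 0-3, 4-6, 7-9 and 10-12 are 0.4, 5.2, 24.2 and 70.2%. Results for the two bands that hold most subjects, from 2,000,000 simulated subjects per arm (mean of five seeds):

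| Scenario | 7-9 band, baseline-adjusted (unadjusted) | 10-12 band, baseline-adjusted (unadjusted) |
|---|---|---|
| Active 2 breaths higher | -11.6 (-13.8) m | -4.7 (-6.0) m |
| Active 1 breath higher | -5.8 (-6.9) m | -2.7 (-3.4) m |
| Active 1 breath lower | +5.9 (+6.9) m | +3.4 (+4.2) m |
| Active 2 breaths lower | +11.6 (+13.8) m | +7.2 (+8.9) m |
| Active 3 breaths lower | +17.4 (+20.6) m | +11.5 (+14.2) m |
| Same dose distribution in both arms, frailty linked to dose in placebo only | +16.4 (+20.5) m | -8.1 (-10.4) m |

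The comparison of whole arms stayed within 0.1 m of the true effect in these scenarios. A rerun with a new seed agreed with the table to within about 0.3 m.

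**What the table shows.** The sign follows the unknown direction of the dose shift. Adjusting for Baseline 6MWD reduces the bias but does not remove it; the reduction depends on how well baseline captures frailty. With a baseline-frailty correlation of -0.3 or -0.7 in place of -0.5, 2 breaths lower gives 12.9 and 8.3 m, or 8.9 and 5.2 m. The last row shows that equal dose distributions in the two arms are no safeguard.

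**When it does not happen.** If dose acts directly on change (5 m per breath) and shares no cause with it, a shift of 2 breaths lower leaves about -1 m in each band.

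**Precision.** At 157 per arm the standard error of a band contrast is 15 to 22 m (7-9) and 9 to 13 m (10-12). One trial could not tell most of these shifts from chance.

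**The case against.** The strongest reply has four parts.

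- *Bias is possible, not certain.* This is true, and the no-shared-cause case shows it. But the documents give no way to tell which case applies, and a check whose error has unknown sign and size cannot confirm or undermine anything.
- *Titration is more uniform than it sounds.* Allocation is blinded, both arms have the same target and maximum, and protocol 6.1 asks for doses to be maximised; considering functional improvement is permitted, not required. This limits dosing driven by outcome. It does not remove differences in tolerability between active drug and placebo, which are enough when frailty affects both dose and walk distance.
- *The magnitudes rest on invented inputs.* They do, and the placebo-only link in particular shows what can happen, not what is likely. The numbers show the mechanism and its scale and predict nothing for this trial.
- *Little depends on it.* The analysis is one of 13 modifications, run as data permit and only after a significant primary result. Others in the list, such as the alternative imputations and the use of off-drug data, do address robustness, and an MMRM is added. This stands and sets the severity.

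It can also be said that a label alone would be enough. A label would remove most of the harm, but a between-arm estimate and p-value by dose would still invite the reading that the label warns against.

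**Conclusion.** The concern holds, at low severity. The SAP presents between-arm contrasts within a post-randomisation variable as robustness evidence, without a caveat, and they cannot serve as such. On the assumed inputs with Baseline 6MWD as covariate, shifts of 1 to 3 breaths in the active arm move the 7 to 9 and 10 to 12 band contrasts by about 3 to 17 m in either direction when the true effect is 0. These sizes rest on an assumed frailty-change correlation of -0.4, an assumed dose distribution and an assumed baseline-frailty correlation of -0.5. The real direction and size cannot be known from the documents. The primary test, alpha, secondary hierarchy and sample size do not use dose and are unaffected.

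**What to change.** - Remove Week 16 study drug dose from the between-arm subgroup list in SAP 8.2 and from the stratified analyses in SAP 10.1.1.3, and state that it is not a row of the forest plot (Figure 14.2.3, for which the SAP gives only a title).
- Keep Table 14.2.1.16 as a within-arm descriptive summary, with no between-arm difference or p-value, and keep Figure 14.2.2 as the display by inhaled treprostinil dose. Label both as non-randomised dose groups.
- In the same edit, say whether subjects off drug at Week 16 belong to the 0 to 3 breath band. SAP 12.1 limits its dosing summaries to subjects still receiving drug; 8.2 and 10.1.1.3 do not say. It matters because subjects imputed as 0 m under Table 8-1 could fall in that band, each with a change of -100 m or lower (0 minus a Baseline 6MWD of at least 100 m, as entry requires).

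The cost is SAP wording and one supportive between-arm display fewer. No data are lost.
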